#### 9.3.2.2 Secondary outcomes

*Databases I/II combined*

Secondary endpoints will include, Rate of exacerbation,

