### 9.3.2 Outcomes

#### 9.3.2.1 Primary outcomes

*(Database I/II combined)*

The primary outcome measure is time to first exacerbation per person. Exacerbations will be defined as either a hospitalization with a primary diagnosis of asthma, an ER visit with a primary diagnosis of asthma, an asthma exacerbation diagnosis recorded (ICD 493.02, 493.12, 493.22, 493.92, J45.21, J45.31, J45.41, J45.51, J45.901). The primary endpoint analysis will be of patients aged 12 years and above.

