### **9.3.3 Covariates**

Other covariates are described in [Table 1](#), including demographic information as available in the dataset as recorded at index date. Comorbidities included in the CCI will be identified during the pre-index period. Other and specific comorbidities such as cardiovascular conditions, cerebrovascular diseases, hypertension, diabetes, metabolic and endocrine comorbidities, anxiety and depression, gastro-esophageal reflux disease, cancer and obesity will also be identified during baseline. Additionally, polypharmacy at baseline, will be identified in the pre-index period. Finally, a composite measure of asthma control status will be made as defined in Table 1, classified as Well and Poor. Asthma Control Test score and eosinophil blood count levels as available, will also be identified at baseline for Cohort II only. We will also record exacerbation rate, resource use parameters, and cost during baseline.

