## **9.7 DATA ANALYSIS**

### **9.7.1 Main analysis**

We will provide the sample attrition at each step of the inclusion-exclusion criteria as well as a baseline demographic and comorbidity breakdown. We will provide a comparative breakdown in baseline measures for the unmatched and matched cohorts to assess if PSM eliminated baseline differences. For the primary endpoints analysis, we will calculate the time to first exacerbation per patient and compare it between the two groups (Tio vs. NonTio). For secondary endpoint analyses we will compare the rate of exacerbation, proportion of patients with exacerbations after 6 months and one year (based on Kaplan Meier estimates), HCRU and average cost during follow-up and compare them between the two groups (Tio vs. NonTio).

The primary outcome of the study will be analyzed using Cox proportional hazard modelling. The secondary outcome of rate of exacerbation per patient will be analyzed using negative binomial regression. This technique works on the assumption that the rate of exacerbation varies among every subject in the study ([P16-06846](#)). Also this model accounts for overdispersion of data which is likely to happen due to variability between the patients. Balance in covariates will be checked after matching. If PSM was able to balance all observed baseline characteristics, the regression models for outcomes will be limited to the databases (IMS and EMR) and to the key independent variable of interest (namely Tio use vs. ICS/LABA dose increase) and model overfitting is not, therefore, of concern. However, if there are unbalanced baseline characteristics, we will include these characteristics in the regression as covariates. For regression model covariate selection we

will also estimate the multicollinearity of covariates by assessing their correlations of independent variables. For example, if comorbidities from the specific list are also included in CCI, they will only be included in the CCI.

In order to handle missing data, in the PSM we will create a category variable (‘missing data’) for each covariate to ensure that patients with that variable and without that variable are respectively matched. Patients with missing prescription data required for classification of the treatment groups will be excluded. Patients with missing lung function scores and ACT scores at baseline and in the follow up period will be excluded from these respective secondary analyses.

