## 9.11 SUBJECTS

1. Patients with least one asthma diagnosis in the inpatient setting or at least two separate instances of asthma diagnosis (separated by at least 30 days) recorded in the outpatient or emergency room setting will be included (ICD 9 CM: 493.xx or ICD 10: J45-J45.999).
2. Patients will be required to be already on ICS/LABA.
3. Patients below the age of 6 years on the ICS/LABAI date will be excluded.
4. Patients will be required to have available records 12 months prior to the index date (6 months will be used if patient exclusions due to this criteria adversely affect the study sample size).
5. Patients with a diagnosis of COPD at any time during the study period will be excluded.
6. Those who are on biologics at baseline will be removed.
7. After the PSM process, unmatched patients will be excluded.

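### The secondary exacerbation rate has no episode rule, so the definition as written lets one attack count two or three times

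*Combined protocol and SAP*

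**What the plan says.** Section 9.3.2.1 sets the event definition: "Exacerbations will be defined as either a hospitalization with a primary diagnosis of asthma, an ER visit with a primary diagnosis of asthma", or "an asthma exacerbation diagnosis recorded" from a list of ICD codes. The third route has no limit on care setting or diagnosis position. The definition is written for the primary outcome: "The primary outcome measure is time to first exacerbation per person".

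Section 9.3.2.2 then adds a recurrent-event outcome: "Secondary endpoints will include, Rate of exacerbation". Section 9.7.1 gives the model: "The secondary outcome of rate of exacerbation per patient will be analyzed using negative binomial regression". Its reason for that model is that "this model accounts for overdispersion of data which is likely to happen due to variability between the patients"; repeat records of one attack are not mentioned. Section 9.3.3 uses the same quantity before index: "We will also record exacerbation rate, resource use parameters, and cost during baseline".

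None of these sections says how records close in time are merged into one attack. The only gap in days between diagnosis records is in section 9.11, where cohort entry can rest on "at least two separate instances of asthma diagnosis (separated by at least 30 days) recorded in the outpatient or emergency room setting". The duplicate checks in sections 9.9 and 9.10 concern patients who appear twice, not events recorded twice.

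**The concern.** A time-to-first analysis uses only the earliest qualifying record, so overlapping record types do no harm there. A count is different. A patient seen in the ER, admitted, and then seen at a visit carrying an exacerbation code meets the definition three times for one attack.

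Three things are at stake. First, absolute rates would describe records, not attacks, and would partly repeat the admissions, ER visits and outpatient visits already counted under health care resource utilization. Second, variation in records per attack adds noise to the counts. Third, if the two groups generate different numbers of records per attack, the rate ratio partly reflects that difference. The two databases may also differ in this respect: section 9.4 describes Database II as claims linked to EMR and provider billing files, and both databases are pooled for shared endpoints. With no rule, two competent analysts could report different rates from the same data.

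**Working it through.** **Inputs.** The plan states no expected rate, sample size or power for the exacerbation rate, so there is no figure of its own to reproduce for this endpoint. The control hazards in section 9.5 do reproduce: −ln(1 − 0.064)/5.5 = 0.0120 per month and −ln(1 − 0.269)/11 = 0.0285 per month (stated as 0.012 and 0.028). Over 12 months the stated hazards give μ = 0.144 and μ = 0.336 attacks per patient. Group sizes are 2,100 Tio and 4,200 NonTio, with a ratio of 0.80 (0.0096/0.012). The following are assumptions, not in the documents: 12 months' follow-up, negative binomial dispersion k = 1, two-sided 5% tests, and every distribution of K, the number of qualifying records per attack.

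**Absolute rate.** If each record is counted, the rate is multiplied by E[K].
- 50/30/20% with 1/2/3 records: E[K] = 0.5 + 0.6 + 0.6 = 1.7
- 70/20/10%: E[K] = 0.7 + 0.4 + 0.3 = 1.4
- 30/40/30%: E[K] = 0.3 + 0.8 + 0.9 = 2.0

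**Precision.** The relative variance (variance over squared mean) of a patient's count is 1/μ + k when attacks are counted, and (1/μ)·E[K²]/E[K]² + k when records are counted. Only the Poisson part is inflated. For 50/30/20%, E[K²] = 0.5 + 1.2 + 1.8 = 3.5, so the factor on that part is 3.5/1.7² = 3.5/2.89 = 1.21.
- μ = 0.144: (6.94 × 1.21 + 1)/(6.94 + 1) = 1.18
- μ = 0.336: (2.98 × 1.21 + 1)/(2.98 + 1) = 1.16

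The total relative variance therefore rises about 16 to 18%, and the standard error about 8 to 9% (√1.16 = 1.08, √1.18 = 1.09).

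**Rate ratio.** Counted ratio = true ratio × E[K] in Tio / E[K] in NonTio. Equal means leave it unchanged. With unequal means and a true ratio of 0.80:
- Tio 1.75, NonTio 1.55: 0.80 × 1.75/1.55 = 0.90
- Tio 1.90, NonTio 1.55: 0.80 × 1.90/1.55 = 0.98
- Tio 1.55, NonTio 1.75: 0.80 × 1.55/1.75 = 0.71

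**Simulation.** 400 runs per scenario, gamma-Poisson attacks, section 9.5 group sizes, robust variance for the log ratio:

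| Scenario | Counted ratio | SE of log ratio | Significant |
|---|---|---|---|
| μ 0.144, true 0.80, one count per attack | 0.80 | 0.081 | 82% for Tio |
| μ 0.144, true 0.80, mean 1.55 in both groups | 0.80 | 0.089 | 70% for Tio |
| μ 0.144, true 0.80, Tio 1.75, NonTio 1.55 | 0.90 | 0.089 | 20% for Tio |
| μ 0.144, true 1.00, Tio 1.75, NonTio 1.55 | 1.13 | 0.083 | 31% against Tio |
| μ 0.336, true 0.80, one count per attack | 0.79 | 0.057 | 99% for Tio |
| μ 0.336, true 0.80, mean 1.55 in both groups | 0.80 | 0.061 | 96% for Tio |

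If every attack gives exactly three records, both rates triple while the ratio and its standard error stay the same. The loss of precision comes from variation in K, not from its size.

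**The case against.** The plan never says that records will be counted separately. Section 9.3.2.1 lists alternative ways to qualify, and section 9.7.1 speaks of a rate of exacerbation, not of records. A sensible programmer might merge records unprompted. This stands as a limit on the wording: the defect is a definition that permits multiple counting, not a stated decision to do it.

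A reader might infer that the treatment comparison is distorted. The documents do not support that. Bias in the ratio needs records per attack to differ by group. Section 9.12 expects Tio patients to be more severe at baseline and in follow-up, and section 9.9 accepts that deteriorating Tio patients may be matched to patients continuing the same high-dose therapy, so a difference is plausible. Neither section sizes it. The matching in Table 1 covers control status and the presence of asthma-related admissions, visits and OCS use, and may reduce it. It need not remove it: Table 1 uses presence, not number, and omits the baseline exacerbation rate.

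Negative binomial regression does absorb extra variation, but it cannot restore lost precision or turn records into attacks.

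Section 9.4 allows secondary outcome measures to be finalized after the data are examined. That is a route to closing the gap, but it supplies no rule and would leave the choice open after the data have been seen. The sentence in section 9.3.2.2 also ends at a comma, so text may be missing there. Sections 9.3.2.1, 9.3.3 and 9.7.1 show no rule either.

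**Conclusion.** The point holds as a gap in the definition of a secondary endpoint that will be formally modelled, and of the matching baseline measure. If the definition is applied as written, absolute rates are inflated by the mean number of records per attack: 1.4- to 2.0-fold under the assumed mixes. Relative variance rises about 16 to 18% for the 50/30/20% mix with dispersion 1 and 12 months' follow-up. The 21% figure applies to the Poisson part alone and should not be read as the total.

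Bias in the rate ratio is conditional. The shifts from 0.80 to 0.90 or 0.98 show how sensitive the ratio is to unequal records per attack; they are not estimates for this study. If Tio attacks generate more records, the bias runs against Tio; if fewer, in its favour.

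Time to first exacerbation and the Kaplan-Meier proportions at 6 months and one year use only the first qualifying record, so the primary result does not depend on an episode rule. The change should be made, but the primary analysis does not hinge on it.

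**What to change.** Define an exacerbation episode before analysis: all qualifying records within a fixed window from the first record (for example 14 days), dated at that first record and counted once. Measuring the window from the first record caps it. Linking records by consecutive gaps would not, and could merge weeks of separate attacks into one. State which period an episode belongs to if it spans the index date.

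Apply the same rule to the baseline rate in section 9.3.3 and to follow-up, in both databases. Use episode counts in the negative binomial model and state a log follow-up offset: section 9.7.1 names none, while section 9.1 lets follow-up run from 30 days with no maximum. Repeat with a 30-day window as a sensitivity analysis. Neither length is derived from the documents; the 30-day gap in section 9.11 confirms an asthma diagnosis at entry and is only an analogy.

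The cost is one definition, a short programming step and one repeat analysis. The downside is that distinct attacks within the window count as one, while a late visit for the same attack beyond it still counts as new. Comparing the two windows shows how much either matters.

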#### Health Care Resource Utilization (HCRU)

HCRU is defined as frequency of hospitalizations, ER visits, and outpatient visits during follow-up, all-cause and asthma related, and the associated costs (medical and pharmacy).

#### *Additional Secondary outcomes Database II*

Where Tio patients and their matched subgroup of NonTio patients both have available lung function test results at baseline and in the follow up period, we will utilize change in lung function (trough FEV1) as a secondary outcome.

Where Tio patients and their matched subgroup of NonTio patients both have available ACT score results at baseline and in the follow up period, we will utilize change in ACT score.

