**Table 1: Matching Parameters**

Variable Name and Type	Description	Applicable to Study Cohort: 1=IMS, 2=EMRClaims+
ICS/LABA dose on ICS/LABAI date	The dose level of the first prescription on the ICS/LABAI date (low, medium, or high)	1 and 2
Demographics (categorical and continuous variables)	Age (10-year increments) and Gender Male/Female), Region (if available, Northeast, Midwest, South, West)	1 and 2
CCI (continuous variable)	Charlson Comorbidity Index score	1 and 2
Specific comorbidities (categorical variables)	Cardiovascular conditions, cerebrovascular diseases, hypertension, diabetes, metabolic and endocrine comorbidities, anxiety and depression, gastro-esophageal reflux disease, cancer and obesity identified using appropriate ICD codes. All above measures will be coded as binary (yes/no) variables.	1 and 2
Medications (categorical variable)	Polypharmacy level matched within a range of 2 drugs (for example, 0-2,3-5,6-8,8-10 and so on).	1 and 2
Asthma Control Status: Well Control or Poor Control (categorical variable)	‘Well Controlled’ if patient has no prescriptions for an OCS, and no asthma-related emergency department visits or hospitalizations other than the first diagnosis recorded in the data extracted (Ref: Stempel JACI 2005). Categories will include Well Controlled and Not Well Controlled.	1 and 2
Hospital admissions Outpatient visits ER visits and OCS use (categorical variables)	Poorly Controlled patients (“Not Well Controlled”) will further be matched based on the presence of asthma-related admissions, outpatient visits, and ER visits or use of OCS during the pre-index period.	1 and 2
Eosinophil levels (EMRClaims+ database only) (categorical variables)	Eosinophil level categories: <150 cells/μL, 151-300cells/μL, 301-400 cells/μL, ≥400 cells/μL (as available)	2
Asthma Control Test (ACT) results (EMRClaims+ database only) (categorical variables)	ACT score categories developed based on data distribution (as available)	2

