## 9.12 BIAS

### Channeling Bias Mitigation

Introduction of channeling bias in this study is highly likely using retrospective claims data based on asthma medication use; patients between the two cohorts may differ in baseline control and severity levels. On aggregate, patients for whom Tiotropium Respimat® 1.25 mcg was added (vs NonTio) are likely to be less well-controlled and more severe both at baseline and during the follow up period. Absent a method to control for this channeling bias, it is likely that placing sicker patients in the Tiotropium Respimat® 1.25mcg group will confound an accurate comparison of cost, resource use, and other outcomes between the groups. Two design features of our study will help mitigate this bias. First, our comparison (NonTio) group will be required to step-up their baseline ICS/LABA dose or have an additional prescription/refill of high-dose-ICS/LABA following the first prescription of baseline high dose ICS/LABA within the study period. Second, we will use Propensity Score Matching (PSM) to match patients on key measures of disease control and severity as listed in [Table 1](#), such as demographics, Charlson Comorbidity Index (CCI) score, specific comorbidities, number of prescriptions (overall and asthma-related medications). This baseline matching strategy will be particularly important to ensure that patients in the TIO group who have a corresponding increase in their ICS dose at or prior to the date of their TIO prescription (for example, if the patient has an exacerbation), will be matched to a corresponding NonTIO patient in terms of increased ICS dose or additional ICS prescription. It should be noted that after the prescription index date for both Tio and NonTio patients, we anticipate changes in ICS medication for patients in both cohorts. These ICS medication changes reflect patient

outcomes in the follow-up period, where patients who encounter exacerbation in either group are likely to see a change in the ICS dose.

As a result, post-index period ICS medication changes will not alter the classification of patient groups nor will it be the basis for exclusion of these patients.

We will conduct 1:2 matching using a nearest neighbour matching approach with a radius of  $0.2 * SD(\log(P))$ . This will be conducted in both databases (IMS: Cohort I and EMRClaims+: Cohort II) separately.

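### FEV1 and ACT changes are analysed only in matched sets where Tio and NonTio members are all measured, but the matching does not secure this, so tested patients can be lost through an untested partner

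*Combined protocol and SAP*

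**What the plan says.** Under the additional secondary outcomes for Database II (section 9.3.2.2), change in trough FEV1 is to be used "Where Tio patients and their matched subgroup of NonTio patients both have available lung function test results at baseline" and in follow-up. Change in ACT score has the parallel condition: "Where Tio patients and their matched subgroup of NonTio patients both have available ACT score results at baseline and in the follow up period". Neither sentence says whether both matched controls must have results or whether one is enough.

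Section 9.12 describes the matching: "We will conduct 1:2 matching using a nearest neighbour matching approach with a radius of" 0.2 SD on the log scale of the score, and "This will be conducted in both databases (IMS: Cohort I and EMRClaims+: Cohort II) separately". No further match is planned for the FEV1 or ACT outcomes.

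Table 1 lists the matching parameters. For Database II it includes baseline ACT in categories. It includes no lung function value and no indicator of having been tested, and nothing about tests after the index date.

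Section 9.7.1 contains two relevant rules. For covariates in the propensity model, a missing-data category is created "to ensure that patients with that variable and without that variable are respectively matched". For the outcomes, "Patients with missing lung function scores and ACT scores at baseline and in the follow up period will be excluded" from the respective secondary analyses; matched partners are not mentioned. The same section plans a comparison of baseline measures in the unmatched and matched cohorts. If matching has balanced all observed characteristics, the outcome models are limited to treatment and database.

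**The concern.** The set-level condition is applied after matching, but the matching was not built to satisfy it. A Tio patient with FEV1 at both times is unusable if the assigned controls were not tested, even when other NonTio patients with a similar score were. The same holds for a tested control whose Tio partner was not tested.

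Two things are at stake. The first is sample size, in outcomes that section 9.9 already expects to be incomplete. The second is comparability. The patients analysed are a subset selected by test availability, and the planned balance check concerns the matched cohort as a whole. Baseline FEV1 is never matched on, so nothing in the plan shows whether the groups start from similar lung function in that subset.

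**Working it through.** The documents give no sample size, power or retention figure for FEV1 or ACT, so there is no plan figure to reproduce.

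**Inputs.** Sets of one Tio and two NonTio patients (section 9.12). Let p be the probability that a patient has the test at both baseline and follow-up. The documents give no value for p; section 9.9 says only that not every Database II patient will have these results. I assume a range for p and, first, independence within a set.

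**Tested patients per set:** 3p.

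**Strict reading (Tio and both controls tested).** A set is usable with probability p³ and then contributes 3 patients. Share of tested patients kept = 3p³ / 3p = p².

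**Lenient reading (Tio and at least one control tested).** The Tio patient is kept with probability p[1 − (1 − p)²] = 2p² − p³. Each tested control is kept if the Tio patient is tested, giving 2p² for the two controls. Share kept = (4p² − p³) / 3p = (4p − p²) / 3.

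| p | strict, p² | lenient, (4p − p²)/3 |
|---|---|---|
| 0.2 | 4% | 25% |
| 0.4 | 16% | 48% |
| 0.5 | 25% | 58% |
| 0.6 | 36% | 68% |
| 0.8 | 64% | 85% |
| 0.9 | 81% | 93% |

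**Check at p = 0.5, per 100 sets.** Tested patients: 300 × 0.5 = 150. Strict: 100 × 0.125 = 12.5 sets, or 37.5 patients; 37.5/150 = 25%. Lenient: 100 × (4 × 0.25 − 0.125) = 87.5 patients; 87.5/150 = 58%.

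**Where half is lost.** Strict: p² = 0.5 gives p = 0.71. Lenient: p² − 4p + 1.5 = 0 gives p = 2 − √2.5 = 0.42. More than half of the tested patients are lost only below these values.

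**Dependence.** If testing clusters within sets, the loss is smaller; with full concordance it is zero.

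**ACT.** Suppose the missing-data category made baseline ACT availability fully concordant within sets. The same formulas then apply to q, the probability of a follow-up score given a baseline score. At q = 0.8, 64% (strict) or 85% (lenient) of those scored at both times are kept. Matching on a single propensity score does not guarantee that concordance, so this is the favourable case. FEV1 has no such provision.

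**The two exclusion rules side by side.** Section 9.3.2.2 makes a patient's inclusion depend on the partners' results. Section 9.7.1 makes it depend on the patient's own results. Under the second rule no tested patient is lost through a partner, but the matched sets are broken. The two rules give different analysis sets.

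**The case against.** The strongest reply has four parts.

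- The plan does try to align availability: the missing-data category is meant to pair patients who have a covariate with others who have it, and baseline ACT is a covariate. This stands for baseline ACT, as an aim rather than a guarantee. It does not reach FEV1 or any follow-up test.
- Section 9.7.1 can be read as exclusion of individual patients, in which case partners are not dropped. That reading is open, but it contradicts section 9.3.2.2, so the analysis set remains undefined.
- Keeping intact sets preserves closeness on the propensity score, and section 9.7.1 provides for adjustment where imbalance is found. A reader might infer that the tested subset is unbalanced; the documents do not show that. What stands is that no check in that subset is stated and that baseline FEV1 is outside the score.
- Section 9.9 concedes smaller samples and limited generalisability, and section 9.4 leaves covariates and secondary outcomes open to revision once missing data have been evaluated. Both are true, but neither settles the rule.

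A reader might also infer that only a handful of usable sets will exist. Scaling 2,100 Tio patients by insured lives gives 2,100 × 0.69/150.69 ≈ 10 to 2,100 × 0.69/40.69 ≈ 36 in Database II. The protocol gives no split by database and also cites more than 20 million EMR for that source, so this is a guess and the point does not rest on it.

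**Conclusion.** The point holds in a limited form. As section 9.3.2.2 is written, tested patients can be lost because a matched partner was untested. This applies mainly to FEV1 and, for ACT, mainly to follow-up scores. The analysis set is described in two incompatible ways, and no balance check is planned in it.

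The loss could be large or modest. Under independence, 25% to 58% of tested patients are kept at 50% availability and 64% to 85% at 80%, depending on whether both controls or one must be tested. It is tempting to conclude that most tested patients are discarded. The documents do not support that: it would require availability below about 0.71 (strict) or 0.42 (lenient), no rate is given, and positive correlation within sets lowers the loss.

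These are secondary outcomes in one database and the primary endpoint is untouched. The change is worth making because it is cheap and removes an avoidable loss.

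**What to change.** 1. Reconcile sections 9.3.2.2 and 9.7.1 so that one rule defines the FEV1 and ACT analysis sets.
2. For each outcome, restrict Database II (Tio and NonTio) to patients with a pre-index test, repeat the 1:2 match within that subset, and check balance there, including the baseline FEV1 or ACT value.
3. Exclude patients with no follow-up test individually rather than by set, and report follow-up availability by group.
4. Adjust the change score for its baseline value.
5. If too few Tio patients remain to refit the propensity model, reuse the existing Database II score and report descriptively with a confidence interval.

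The cost is two extra matching runs in Database II, a balance table for each, and a short addition to section 9.7.1. There are three drawbacks. The FEV1 and ACT samples no longer nest in the primary matched sample. Some tested patients may still find no match within the radius. Loss from missing follow-up tests remains, because re-matching on pre-index testing cannot recover it.

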### **9.1 STUDY DESIGN**

Data extraction from both databases (I and II, see [section 9.4](#)) will be conducted by

. All patients will be required to have a prescription for ICS/LABA therapy [e.g. Advair (Diskus and HFA), Airduo, Breo, Dulera, or Symbicort]. The date of the first prescription of ICS/LABA within the study period (Jan 1st 2016 to Nov 30th 2018) will be defined as ICS/LABA-initiation (ICS/LABAi) date. This baseline cohort will then be followed to identify two cohorts (two arms of the study). One cohort that receives a prescription for Tiotropium Respimat® 1.25 mcg (on top of baseline ICS/LABA) will be classified as the ‘Tio’ group, and the second cohort that receives a “step-up” from baseline low-dose ICS/LABA to medium/high dose ICS/LABA or from baseline medium dose ICS/LABA to high dose ICS/LABA or an additional prescription/refill of high-dose-ICS/LABA following the first prescription of baseline high dose ICS/LABA within the study period, will be classified as the ‘NonTio’ group. The date of the first prescription for Tiotropium Respimat® 1.25 mcg in the ‘Tio’ group will be defined as the index date for the ‘Tio’ group. Similarly the date of the first prescription for a “step-up” from baseline low-dose ICS/LABA to medium/high dose ICS/LABA or from baseline medium dose ICS/LABA to high dose ICS/LABA or an additional prescription/refill of high-dose-ICS/LABA following the first prescription of baseline high dose ICS/LABA (evidenced by at least 90-days of prescription utilization) within the study period will be defined as the index date for the ‘NonTio’ group.

Patients will be required to have a minimum follow-up period of 30 days after the index date for the analyses of the primary endpoint with no limit on the maximum period (this 30-day minimum follow-up period requirement will be waived in a sensitivity analysis). Subject to sample size requirements, patients will be required to have available records for at least 12 months prior to the index date to ensure no prior use of Tiotropium Respimat® and to establish baseline patient characteristics. This 12-month period prior to the index date will be defined as the pre-index period.

Figure 9.1.1 Study Design

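### Change in FEV1 and ACT (Database II) has no assessment window or value-selection rule, and the continuous baseline value is absent from the model by default

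*Combined protocol and SAP*

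**What the plan says.** Section 9.3.2.2 (additional secondary outcomes, Database II) defines both outcomes in two sentences. For FEV1 the outcome is stated as "we will utilize change in lung function (trough FEV1) as a secondary outcome". It applies to a Tio patient and the matched NonTio patients only when these "both have available lung function test results at baseline and in the follow up period". For ACT, the condition is that they "both have available ACT score results at baseline and in the follow up period, we will utilize change in ACT score". No time point, window, rule for repeat tests or model is given.

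The rest of the protocol supplies the following:

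- **Follow-up (9.1).** At least 30 days for the primary endpoint, "with no limit on the maximum period". Nothing separate is set for FEV1 or ACT.
- **Baseline (9.1).** "This 12-month period prior to the index date will be defined as the pre-index period". How close to index the baseline test must fall is not stated.
- **Matching (Table 1).** ACT score is listed in categories, as available, for Database II. There is no lung-function row. Age is in 10-year increments.
- **Models (9.7.1).** Cox regression is named for the primary outcome and negative binomial regression for the exacerbation rate. If matching balances the observed baseline characteristics, "the regression models for outcomes will be limited to the databases (IMS and EMR) and to the key independent variable of interest". Characteristics left unbalanced are added as covariates.
- **Age.** Section 9.11, item 3: "Patients below the age of 6 years on the ICS/LABAI date will be excluded". The limit of 12 years and above in 9.3.2.1 is stated for the primary endpoint analysis only.

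**The concern.** FEV1 and ACT are the study's only lung-function and symptom-score outcomes. As they are written, three things are left open.

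1. **Interval.** One patient's change may span a month and a matched patient's more than two years. Time since index is then part of the result. Someone choosing among several tests after seeing the data would have wide freedom.
2. **Starting value.** A change score without the baseline value in the model can pick up regression to the mean if the arms start at different levels, and it is less precise than an adjusted analysis even if they do not.
3. **Age, for FEV1 only.** FEV1 in litres rises with growth in children and falls with age in adults. Patients from age 6 are included here, and a 10-year band can put children at quite different stages of growth together.

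Also, FEV1 is labelled trough, which implies a time relative to dosing. Sections 9.4 and 9.10 describe lung-function results held in an EMR database, and nothing ties a test to dose timing.

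**Working it through.** The documents give no sample size, SD, effect size or power for FEV1 or ACT, so there is no figure to reproduce. The check is a reading of the text followed by an illustration with assumed inputs.

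**Longest possible interval.** The study period in 9.1 runs from 1 January 2016 to 30 November 2018, which is 35 months. Follow-up after index can therefore reach about 35 months at most.

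**What the default model contains.** Section 9.7.1 leaves database and treatment. These outcomes exist in Database II only, so the database term is constant and treatment alone remains.

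**Can the fallback for unbalanced characteristics reach the baseline value?** For ACT, yes, as a Table 1 variable in categories. For FEV1, only if someone chooses to treat it as a baseline characteristic: neither Table 1 nor the covariate list in 9.3.3 names it.

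**Does matching settle it?** Matching and the balance check concern the full matched cohorts. These outcomes use the subset of matched sets with tests at both times. Keeping matched sets together does not guarantee balance in that subset, least of all on FEV1, which is not in the propensity score.

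**Regression to the mean.** Let d be the baseline difference between arms in SD units and r the baseline-to-follow-up correlation, with equal SDs at both times. If both arms regress to a common mean and there is no treatment effect, the difference in mean change is (1 − r) × d, in favour of the arm that starts worse. With d = 0.2 (assumed):

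- r = 0.5: 0.5 × 0.2 = 0.10 SD
- r = 0.8: 0.2 × 0.2 = 0.04 SD
- d = 0: bias is 0 for any r

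**Precision with balanced baselines.** With unit variance at each time, the change score has variance 2(1 − r) and the baseline-adjusted value 1 − r². The ratio is (1 − r²) / [2(1 − r)] = (1 + r)/2:

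- r = 0.5: 0.75, a 25% reduction
- r = 0.8: 0.90, a 10% reduction

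**Test timing, FEV1 only.** Bias = annual slope × difference between arms in mean test time. For an assumed difference of 0.5 year:

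- adult decline of 30 to 50 mL/year (assumed): 15 to 25 mL
- childhood growth of 200 to 300 mL/year (assumed): 100 to 150 mL among children
- no difference in timing or age mix: no bias, only added noise

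**The case against.** The strongest defence is that baseline is not ignored and that the bias is conditional.

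- **ACT is handled.** A reader might infer that no baseline adjustment is planned for either outcome. That is not so: ACT is matched in categories where available and would enter the regression if unbalanced. What stands is that category handling can leave residual differences, and that FEV1 has no named provision.
- **Section 9.12 does not show that the analysed arms differ.** Its statement that Tio patients "are likely to be less well-controlled and more severe both at baseline and during the follow up period" might be read as proof that raw change will favour Tio. It describes patients before mitigation, and the section goes on to name the comparator design and matching as remedies. It also describes a difference that persists. If the arms differ by d at both times, raw change shows no difference, while the adjusted analysis gives d − r × d = (1 − r)d, or 0.04 to 0.10 SD against Tio for the same inputs. In non-randomised groups, therefore, adjustment does not always remove bias. This stands, and it is why the unadjusted change should also be reported.
- **Growth and decline are limited in reach.** They do not concern ACT, and they bias the FEV1 comparison only if age or test timing differs by arm. Age band and gender are matched, and the approval for ages 6 to 11 dates only from February 2017 (section 7).
- **Silence is not a rule.** The protocol never says that any follow-up value will do; it simply does not exclude it.
- **The setting is secondary.** Section 9.4 allows secondary measures to be finalised after missing data are reviewed, and 9.9 warns about sample size and rules out effectiveness claims. Nor are these the only clinical outcomes, since exacerbation is the primary one. This lowers the stakes but does not supply a window or a model.

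**Conclusion.** The concern holds in a limited form. The plan gives FEV1 and ACT no assessment window, no value-selection rule and no model of their own. Baseline FEV1 is neither matched nor a named covariate, baseline ACT is used only in categories as available, and the continuous baseline value is absent by default.

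The size is modest and conditional. Bias is 0.04 to 0.10 SD if the tested subset differs by 0.2 SD at baseline, r lies between 0.5 and 0.8, and both arms regress to a common mean. The values of d and r are assumptions, not figures from the protocol. The loss of precision, 10 to 25% of residual variance over the same r, does not need an imbalance. Growth and decline add noise to FEV1, and add bias only if age or test timing differs by arm.

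The documents do not support saying that the comparison will favour Tio, or that baseline adjustment is a complete cure. They do support a change before analysis: it is cheap, and it closes choices that could otherwise be made after the results are seen. The primary outcome is not affected.

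**What to change.** In 9.3.2.2 and 9.7.1:

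1. Analyse the follow-up value of FEV1 and of ACT by linear regression on treatment, always adjusted for the patient's own continuous baseline value, age, and time from index to test, whether or not matching appears balanced.
2. State one follow-up window, one baseline window and one rule for choosing among repeat tests, the same for both arms. A value closest to 6 months within 3 to 12 months after index is one possibility; the exact limits are a matter of preference, but they need fixing in advance.
3. For FEV1, use percent predicted if it is recorded, which the documents do not confirm. Otherwise apply the age-12 limit already used for the primary endpoint, or report adults separately.
4. Drop the word trough.
5. Report the unadjusted change as a sensitivity analysis, because the groups are not randomised and the two analyses rest on different assumptions.
6. Show baseline FEV1 and ACT by arm in the subset actually analysed.

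The cost is some wording and a few lines of code on data already planned for extraction. Patients with no value inside the windows drop out of these secondary analyses.
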